To evaluate the humoral immune response to RSVPreF3 OA investigational vaccine when co-administered with the first dose of HZ/su vaccine or administered alone.	
 
RSV-A neutralizing titers expressed as GMT at pre-vaccination and at 1-month after the RSVPreF3 OA investigational vaccine dose.
 
RSV-A neutralizing titers expressed as MGI at 1-month after the RSVPreF3 OA investigational vaccine dose.
 
RSV-B neutralizing titers expressed as GMT at pre-vaccination and at 1-month after the RSVPreF3 OA investigational vaccine dose.
 
RSV-B neutralizing titers expressed as MGI at 1-month after the RSVPreF3 OA investigational vaccine dose.
 

To evaluate the safety and reactogenicity following administration of the RSVPreF3 OA investigational	
 
Percentage of participants reporting each solicited administration site and systemic
 

Objectives	Endpoints
vaccine and the HZ/su vaccine, co-administered or administered alone.	
event with onset within 7 days after vaccine administration (i.e., the day of vaccination and 6 subsequent days).
 
 
Percentage of participants reporting unsolicited AEs with onset within 30 days after vaccine administration (i.e., the day of vaccination and 29 subsequent days).
 
Percentage of participants reporting all SAEs after vaccine administration (Day 1) up to study end (6 months after last vaccination).
 
Percentage of participants reporting all pIMDs after vaccine administration (Day 1) up to study end (6 months after last vaccination).
 

Abbreviations: AE=adverse event; CI=confidence interval; gE=glycoprotein E; GMC=geometric mean concentration; GMT=geometric mean titer; HZ/su=herpes zoster recombinant subunit; MGI=mean geometric increase; OA=older adult; pIMD=potential immune-mediated disease; RSV=respiratory syncytial virus; SAE=serious adverse event.

\* Zoster and RSV-A related endpoints will be assessed as co-primary. RSV-B related endpoints will be assessed as sequential to the success of Zoster and RSV-A.

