### 4.4 End of Study Definition

A participant is considered to have completed the study if he/she returns for the last visit as described in the protocol.

End of Study is the last subject last visit (LSLV) (contact at 6 months post-last dose).

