Secondary	RSVPreF3 OA (one dose) and HZ/su (two doses) co-administered (Co-Ad) or received separately (Control)	Adults aged $\geq 50$ YOA	Solicited systemic event within 7 days after each vaccine administration	1. eDiary not completed on each day	1. Missing data won't be imputed. Compliance to eDiary will be captured	Percentage and exact 95% CIs of participants with solicited systemic events within 7 days after each vaccine administration (Days 1-7 after each vaccine, HZ/su and RSVPreF3 OA [i.e., date of RSVPreF3 OA vaccine administration for Control group

						becomes Day 1 for recording events within 7 days]).
Secondary	RSVPreF3 OA (one dose) and HZ/su (two doses) co-administered (Co-Ad) or received separately (Control)	Adults aged $\geq 50$ YOA	Each unsolicited adverse event within 30 days after each vaccine administration	1. Permanently discontinued from study due to any reasons prior to Day 31	1. Missing data won't be imputed. Summaries will present the actual data	Percentage and exact 95% CIs of participants with unsolicited adverse events within 30 days after each dose/the dose of study intervention (Days 1-30 after each vaccine, HZ/su and RSVPreF3 OA [i.e., date of RSVPreF3 OA vaccine administration for Control group becomes Day 1 for recording events within 30 days])
Secondary	RSVPreF3 OA (one dose) and HZ/su (two doses) co-administered (Co-Ad) or received separately	Adults aged $\geq 50$ YOA	Each serious adverse event (SAE) up to study end (6 months after last vaccination)	1. Permanently discontinued from study due to any reasons prior to end of study	1. Missing data won't be imputed. Summaries will present the actual data	Percentage and exact 95% CIs of participants with all SAEs after last dose of study intervention up to study end (Days 1-183 after each vaccine [i.e., date of RSVPreF3 OA vaccine administration for Control

	(Control)					group becomes Day 1 for recording events within 6 months]).

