Secondary	RSVPreF3 OA (one dose) and HZ/su (two doses) co-administered (Co-Ad) or received separately (Control)	Adults aged $\geq$ 50 YOA	Each Potential Immune-Medicated Disease (pIMD) event up to study end (6 months after last vaccination)	1. Permanently discontinued from study due to any reasons prior to end of study	1. Missing data won't be imputed. Summaries will present the actual data	Percentage and exact 95% CIs of participants with all pIMDs up to study end (Days 1-183 after each vaccine [i.e., date of RSVPreF3 OA vaccine administration for Control group becomes Day 1 for recording events within 6 months])

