**Table B: Study Groups**

Study groups	Number of participants	Age (min)	Study interventions
Co-Ad	265	≥ 50 years	RSVPreF3 OA and first of two doses of HZ/su vaccine co-administered, second dose of HZ/su administered separately
Control	265	≥ 50 years	One dose of RSVPreF3 OA investigational vaccine and two doses of HZ/su vaccine all administered separately

[figure not shown]
The total duration of the study participation is the same for the 2 study intervention groups:

- Co-Ad study intervention group: Total duration is approximately 8 months. There will be 4 study visits on site: Visit 1 on Day 1, when the participants receive study intervention (both RSVPreF3 OA and HZ/su as co-administered), Visit 2 on Day 31 when blood sampling for RSVPreF3 OA vaccine antibody testing will be performed, Visit 3 (Day 61) in which the second dose of HZ/su vaccine will be administered, and Visit 4 (Day 91) when blood sampling for HZ/su vaccine antibody testing will be performed. A safety follow-up visit will be made to the participant on Day 243 (i.e., 6 months after last vaccine is received) via telephone or by any other convenient means of communication.
- Control study intervention group: Total duration is approximately 8 months. There will be 4 study visits on site: Visit 1 on Day 1, when the participants receive HZ/su vaccine, Visit 2 on Day 31 when the participants receive RSVPreF3 OA vaccine, Visit 3 on Day 61 when HZ/su vaccine will be administered and blood sampling for RSVPreF3 OA vaccine antibody testing will be performed, and Visit 4 (Day 91) when blood sampling for HZ/su vaccine antibody testing will be performed. A safety follow-up visit will be made to the participant on Day 243 (i.e., 6 months after last vaccine is received) via telephone or by any other convenient means of communication.

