### 6.1. Reference Start Date and Study Day

Study Day will be calculated from the reference start date and will be used to show start / stop day of assessments and events. It will appear in every listing where an assessment date or event date appears.

Reference start date is defined as the day of the first dose of each study vaccination, which is Day 1 for all participants.

If the date of the event is on or after the reference date, then:

[figure not shown]
- Study Day = (date of event – reference date) + 1.

If the date of the event is prior to the reference date, then:

- Study Day = (date of event – reference date).

In the situation where the event date is partial or missing, Study Day, and any corresponding durations will appear partial or missing in the listings unless otherwise stated.

CCI

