### **16.1.6. pIMDs**

For analysis of pIMDs, the reporting period will start at vaccination and will end at approximately 6 months post-last vaccination (i.e., day of last vaccination+[180-210]. pIMDs will be summarized by MedDRA SOC, HLT and PT. pIMDs will be summarized and listed as follows:

CCI

- The number and percentage of participants, with exact 95% CIs, with at least one report of pIMD (all pIMDs, causally related separately) with onset after each vaccine administration up to study end (i.e. 6 months post-last vaccination) will be summarized.
- All pIMDs will also be described in detail in a listing and a tabulated listing of pIMDs leading to discontinuation of study will be provided. Classification by new onset vs exacerbations of pIMDs will also be presented.
- The number and percentage of participants, with exact 95% CIs, with at least one report of neurological demyelinating pIMD with onset within 30 days of any dose will be summarized. This summary will be repeated for serious neurological demyelinating pIMDs with onset after each vaccine administration up to study end.
- Subgroup analysis will be created for the serious events up to study end (6 months after last dose) split by age category, race, ethnicity and gender.

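### The SAE and pIMD rows of SAP 2.4 stop counting at Day 183 after each vaccine, which contradicts SAP 16.1.5/16.1.6 and the 180-210 day study-end contact

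*SAP*

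**What the plan says.** The passages that set the end of the SAE and pIMD window are these.

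- **SAP 2.4, population-level summary cells.** The pIMD row counts "all pIMDs up to study end (Days 1-183 after each vaccine". The SAE row counts "all SAEs after last dose of study intervention up to study end (Days 1-183 after each vaccine". In both, a bracket makes the RSV vaccination date Day 1 for the Control group.
- **SAP 2.4, variable column.** The pIMD row reads "event up to study end (6 months after last vaccination", with no day number. The SAE row has the same limit.
- **Protocol Table 6.** The endpoint is "Percentage of participants reporting all pIMDs after vaccine administration (Day 1) up to study end (6 months after last vaccination", and the SAE endpoint is parallel. The endpoint list in SAP 16 repeats both without a day limit.
- **SAP 16.1.6.** The pIMD reporting period "will end at approximately 6 months post-last vaccination (i.e., day of last vaccination+[180-210" days. SAP 16.1.5 gives the same end for SAEs.
- **Protocol Tables 3-4 and SAP Tables C-D.** The closing contact is planned 180 days after Visit 3, with 180-210 days allowed. Protocol 4.4 ties study end to that contact: "End of Study is the last subject last visit (LSLV) (contact at 6 months post-last dose".
- **SAP 3.1.** "A safety follow-up visit will be made to the participant on Day 243 (i.e., 6 months after last vaccine is received".
- **SAP 6.1.** "Reference start date is defined as the day of the first dose of each study vaccination, which is Day 1 for all participants". One is added to the elapsed days from the reference date onward.

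**The concern.** The 2.4 cells treat study end and Day 183 as the same day, but most of the permitted contact window lies after Day 183. The contact asks about any SAE or pIMD since the last dose (protocol 8.2.2). Take a pIMD that starts on Day 200 after the last dose and is reported at a contact on Day 205. It has been collected as intended and lies inside protocol Table 6, the row's own variable column and SAP 16.1.6. It lies outside the 2.4 summary cell.

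The SAP presents 2.4 as the estimands for regulatory decisions, so the cells are not background text. SAP 3.3 declares no changes to the protocol-defined analyses, so Day 183 is not a declared departure either. No sentence says whether 2.4 or Section 16 governs.

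At stake is whether a late event is counted in the reported percentage. pIMDs are the only adverse events of special interest (protocol 8.3.8) and a listed potential risk for both vaccines (protocol Table 5). With about 265 participants per group, one event is 1/265, or about 0.4 percentage points.

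**Working it through.** **Inputs.** Summary window: Days 1-183 (SAP 2.4). Contact: 180-210 days after Visit 3 (protocol Tables 3-4, SAP Tables C-D). Planned last dose: Day 61. Nominal contact: Day 243 (SAP 3.1). Day count: elapsed days + 1 (SAP 6.1).

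**1. Where Day 183 comes from.** Re-number the nominal contact with the last dose as Day 1: 243 - 61 + 1 = 183. The cut-off reproduces exactly, so it is the SAP's own nominal six months. That nominal day does not match the planned interval: 61 + 180 = Day 241, 2 days earlier.

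**2. Contact window in the same numbering.** Earliest: 180 + 1 = Day 181. Latest: 210 + 1 = Day 211.

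**3. Gap after the last dose.** 211 - 183 = 28 days (Days 184-211), or 28/211 = 13.3% of follow-up after the last dose, for a contact on the last permitted day. A contact by Day 183 loses nothing. Of the 31 permitted contact days (181 to 211), 28 fall after Day 183.

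**4. Average gap, under an assumption.** The documents do not give the distribution of contact dates. If contacts were spread evenly, the mean loss would be (1 + 2 + ... + 28)/31 = 406/31 = 13.1 days, out of a mean of 196 days, or 6.7%. The range is 0 to 28 days.

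**5. Gap after earlier doses, if each vaccine has its own 183-day window.** A window opened on study day d closes on study day d + 182.

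| Dose | Window closes | Study end | Gap (days) |
|---|---|---|---|
| Visit 1 doses, planned visits | Day 183 | Day 241-271 | 58-88 |
| Visit 1 doses, Visit 3 at +84 days (Day 85) | Day 183 | Day 265-295 | 82-112 |
| Control RSV dose at Day 31, planned visits | Day 213 | Day 241-271 | 28-58 |
| Second HZ/su dose at Day 61 | Day 243 | Day 241-271 | 0-28 |

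For the last row, a contact on Day 241 comes 2 days before the window closes, so nothing collected is cut. The larger gaps apply to summaries tied to a given earlier dose. A summary that accepts an event inside any dose's window is limited only by the last dose.

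**The case against.** The strongest reply is that the endpoint has no Day 183 limit. Protocol Table 6, the variable column of the same rows and SAP 16 all run to study end, and the number appears only as a gloss in the summary cells. SAP 16.1.5 and 16.1.6, which specify the tables, already end the period 180-210 days after the last vaccination. All SAEs and all pIMDs are listed whatever window a table uses. The summaries of related and fatal SAEs and of related pIMDs are specified in Section 16, not in the 2.4 rows. Safety is descriptive, with no between-group comparison (SAP 16). The 28 days is a worst case, and the planned contact on Day 181 loses nothing.

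All of that stands. A reader might infer from the 2.4 cells that late events fall outside the endpoint or are lost to the trial. The documents do not support that. Such an event drops out of a percentage only if the 2.4 cell is programmed in preference to Section 16. Nor do the documents give an expected SAE or pIMD rate, so how much one omitted event would matter cannot be stated.

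The reply does not remove the contradiction. The two windows cannot both be programmed for the same percentage, and the reader has to guess that Section 16 governs.

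**Conclusion.** SAP 2.4 contradicts itself, protocol Table 6, SAP 16.1.5/16.1.6 and the contact interval on when SAE and pIMD counting ends. Programmed literally, the 2.4 cells would omit onsets in 0 to 28 days of collected follow-up after the last dose, depending on the contact date. Summaries tied to a Visit 1 dose would omit more, up to 112 days within the permitted visit windows. This rests on the Day 1 convention of SAP 6.1 and on contacts made within the allowed interval.

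The effect is confined to descriptive secondary safety percentages. A reader should not conclude that the protocol endpoint has been shortened, that events would go unreported, or that the non-inferiority conclusions are touched. It is still worth correcting, because the cut-off sits in the estimand table, is not declared as a change, and bears on the trial's only events of special interest.

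**What to change.** - In the SAE and pIMD rows of SAP 2.4, replace the day range and its Control-group bracket with one window: onset from first vaccination (Day 1) up to the study-end contact, 180-210 days after the last vaccination. This matches protocol Table 6 and SAP 16.1.5/16.1.6.
- In the SAE row, also reconcile the two starting points. The cell refers both to the period after the last dose and to each vaccine, while protocol Table 6 starts at Day 1.
- Align Day 243 in SAP 3.1 with the contact interval in Tables C-D.
- Confirm that the SAE and pIMD table programs use the reconciled window.

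The cost is SAP wording and a check of the table specifications. The data are already collected, and neither sample size nor the testing sequence changes.

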## 2.5. Sample size determination

The target enrollment will be approximately 530 participants (approximately 265 in the Co-Ad group and approximately 265 in the Control group) to obtain approximately 450 evaluable participants (approximately 225 in the Co-Ad group and approximately 225 in Control group) for the evaluation of the primary objectives, assuming that approximately 15% of the enrolled participants will not be evaluable (participants withdrawn or excluded from the PPS).

Participants who withdraw from the study will not be replaced.

Each objective will be evaluated with a nominal type I error of 2.5%.

**Table A: Overall Power to Demonstrate Primary Non-Inferiority Objectives: Assuming 225 Evaluable Subjects in Each Group**

Endpoint	Standard deviation of $\log_{10}$ concentration	Reference ratio	Non inferiority margin	Type II error	Power
HZ/su vaccine Non-inferiority* (1-sided test with alpha=2.5%)					
GMCs Anti-gE ELISA Ab	0.35	1.05	1.5	0.3%	99.7%
RSVPreF3 OA investigational vaccine Non-inferiority* (1-sided test with alpha = 2.5%)					
GMTs RSV-A neutralizing titer	0.45	1.05	1.5	4.6%	95.4%
GMTs RSV-B neutralizing titer	0.45	1.05	1.5	4.6%	95.4%
Global Power and Global Type II error				9.5%	90.5%

Abbreviations: Ab=antibody; ELISA=enzyme linked immunosorbent assay; gE=varicella zoster virus -glycoprotein

CCI

E; GMC=geometric mean concentration; GMT=geometric mean titer; HZ/su=herpes zoster/subunit; RSV-A=respiratory syncytial virus subtype A; RSV-B=respiratory syncytial virus subtype B.

\*Pass 2019 alpha = 2.5%, Two-Sample T-Tests for Non-Inferiority Assuming Equal Variance and Equal mean, Power = 100-the Type II error (Beta). The Global Type II error (Beta) has been adjusted using Bonferroni's method (Global Type II error = sum of the individual Type II errors).

For RSVPreF3 OA investigational vaccine: non-inferiority limit = 1.5 ( $\log_{10}[1.5] = 0.176$ )

For HZ/su vaccine: non-inferiority limit = 1.5 ( $\log_{10}[1.5] = 0.176$ )

Reference Ratio= 1.05 ( $\log_{10}[1.05] = 0.021$ )

Considering a slight interference of 1.05 for the reference ratio in favor of the control group versus Co-Ad group with a common population standard deviation of 0.45 for the  $\log_{10}$  transformed RSV-A/RSV-B neutralizing titer and 0.35 for the  $\log_{10}$  transformed HZ/su anti-gE Ab GMC, the study has at least 90.5% power to meet the primary objectives.

[figure not shown]
### 3. STUDY DESIGN

#### 3.1. General Description

This is a phase III, open-label, randomized, controlled, multi-country study in medically stable older adults of  $\geq 50$  YOA with two parallel groups. Participants will be randomly assigned to 2 study groups at Visit 1 (Day 1):

- Co-administration (Co-Ad) group: Study interventions will be administered on Visit 1 (Day 1) in which participants will receive both HZ/su vaccine and RSVPreF3 OA investigational vaccine; and on Visit 3 (Day 61) in which the second dose of HZ/su vaccine will be administered. A total of four site visits (Visit 1 [Day 1], Visit 2 [Day 31], Visit 3 [Day 61] and Visit 4 [Day 91]) and a remote contact 6 months post-last vaccination are needed.
- Control group: Study interventions will be administered on Visit 1 (Day 1) in which participants will receive HZ/su vaccine, Visit 2 (Day 31) in which participants will receive RSVPreF3 OA investigational vaccine; and Visit 3 (Day 61) in which participants will receive the second dose of HZ/su vaccine. A total of four site visits (Visit 1 [Day 1], Visit 2 [Day 31], Visit 3 [Day 61] and Visit 4 [Day 91]) and a remote contact 6 months post-last vaccination are needed.

CCI

**Figure A: Study Schema**

Abbreviations: AE=Adverse Event; Co-Ad group=Co-Administration group; D=Day; Hz/su=herpes zoster recombinant subunit; GSK=GlaxoSmithKline; N=Number of participants; pIMD=potential Immune-Mediated Disease; RSV=RSVPreF3 OA investigational vaccine; SAE=Serious Adverse Event.

Medically stable older adults  $\geq 50$  YOA will be enrolled in this study according the inclusion and exclusion criteria (see protocol Section 5.0). Approximately 530 participants will be randomly assigned to the 2 study intervention groups in a 1:1 ratio prior to intervention to provide approximately 265 enrolled participants in each study intervention group.

The randomization algorithm will use a minimization procedure accounting for age (50-59, 60-69, or  $\geq 70$  years) and center. Minimization factors will have equal weight in the minimization algorithm. Participants will be enrolled in 3 age categories with a balance between males and females. It is intended to enroll:

- Approximately 30% of participants 50 to 59 YOA, approximately 30% of participants 60 to 69 YOA, and approximately 25% of participants  $\geq 70$  YOA. The remaining 15% will be distributed freely across the three age categories.
- Approximately 40% of participants from each sex. The remaining 20% can be distributed freely between the 2 sexes.

**Table B: Study Groups**

Study groups	Number of participants	Age (min)	Study interventions
Co-Ad	265	≥ 50 years	RSVPreF3 OA and first of two doses of HZ/su vaccine co-administered, second dose of HZ/su administered separately
Control	265	≥ 50 years	One dose of RSVPreF3 OA investigational vaccine and two doses of HZ/su vaccine all administered separately

[figure not shown]
The total duration of the study participation is the same for the 2 study intervention groups:

- Co-Ad study intervention group: Total duration is approximately 8 months. There will be 4 study visits on site: Visit 1 on Day 1, when the participants receive study intervention (both RSVPreF3 OA and HZ/su as co-administered), Visit 2 on Day 31 when blood sampling for RSVPreF3 OA vaccine antibody testing will be performed, Visit 3 (Day 61) in which the second dose of HZ/su vaccine will be administered, and Visit 4 (Day 91) when blood sampling for HZ/su vaccine antibody testing will be performed. A safety follow-up visit will be made to the participant on Day 243 (i.e., 6 months after last vaccine is received) via telephone or by any other convenient means of communication.
- Control study intervention group: Total duration is approximately 8 months. There will be 4 study visits on site: Visit 1 on Day 1, when the participants receive HZ/su vaccine, Visit 2 on Day 31 when the participants receive RSVPreF3 OA vaccine, Visit 3 on Day 61 when HZ/su vaccine will be administered and blood sampling for RSVPreF3 OA vaccine antibody testing will be performed, and Visit 4 (Day 91) when blood sampling for HZ/su vaccine antibody testing will be performed. A safety follow-up visit will be made to the participant on Day 243 (i.e., 6 months after last vaccine is received) via telephone or by any other convenient means of communication.

### 3.2. Schedule of Events

Schedule of events can be found in Section 1.3 of the protocol.

CCI

### **3.3. Changes to Protocol Defined Analyses**

No changes.

## **4. PLANNED ANALYSES**

The following analyses will be performed for this study:

- First Analysis
- End of Study (EOS) Analysis

All planned analyses identified in this SAP will be performed by IQVIA Biostatistics following Sponsor Authorization of this SAP, Database Lock and Sponsor Authorization of Analysis Sets.

There will be no Data Monitoring Committee (DMC) meetings for this study.

### **4.1. Interim Analysis**

There will be no interim analyses for this study.

### **4.2. First Analysis**

[figure not shown]
The first analysis, including reactogenicity, safety, and final immunogenicity data, is planned when data for at least primary and secondary endpoints up to and including Visit 4 (Day 91) for the Co-Ad and the control group, are available for all participants.

